#### Measurement Protocols

**Questionnaires:** Before and after the intervention participants will complete questionnaires on general health and lifestyle (IPAQ). In addition, participants' diet will be assessed using a standardized semi-quantitative food frequency questionnaire (FFQ). Subjects will also be administered a FFQ to evaluate nitrate intake. Cognitive tests (MMSE, TMT A and B) will also be administered at baseline and end of the study.

**Body composition:** Measurements will be performed at baseline and at the end of the 14-day interventions. Body weight, height and waist and upper-arm circumferences will be measured using standardised protocols.

**Resting blood pressure:** At baseline and end of the study resting blood pressure will be measured in triplicate using a manual BP monitor. Before the measurement participants will be invited to rest for at least 15 minutes. An appropriate cuff size will be utilised for the measurement of each subject which will be used for all other measurements of BP.

**Endothelial Function:** All the measurements will be undertaken in a temperature-controlled measurement room ( $\sim$ 23  $\pm$  1  $^{\circ}$ C). Each subject will be invited to lie supine for a 5 min rest period. A laser Doppler device will be used to measure microcirculatory blood flow.

**Hand-grip strength:** Hand-grip strength will be assessed in both arms at baseline and after intervention to measure the maximum isometric strength of the hand and forearm muscles. A lightweight and portable dynamometer will be used. The researcher will follow a specific protocol for the measurement of hand-grip strength (i.e. allowing one practice trial, and then record the best of three attempts with 30 seconds rest between each of these).

**Cognitive tests:** All participants will complete a short battery of cognitive tasks that includes Mini Mental State Examination and the Trail Making Test [TMT Parts A and B].

**Blood tests:** Fasting blood tests will be performed by each participant before and after the intervention.

**Urine and saliva collection:** A spot urine sample will be collected in the morning (not first void) at the beginning and end of the intervention for the measurement of nitrate excretion. Stimulated saliva sample will be collected in 1.5ml eppendorf tubes. Samples will be stored at -20°C until analyses

**Dietary nitrate intake:** It is essential to modify the diet to restrict nitrate intake in order to standardise the effects of the diet across the three different interventions as well as to increase the likelihood of detecting unconfounded effects of physical activity and nitrate supplementation on the main outcomes. Human exposure to nitrate occurs primarily through the diet because nitrate occurs in both plants and water. Nitrate is used as a preservative in cured meat but fresh meat contains little nitrate. Fruit and grains have a small impact on dietary intake of nitrate and the dietary advice offered will be recent reports on nitrate content of foods. Therefore diets will be standardized for the consumption: vegetables with high nitrate content (rocket, spinach, cabbage, beet root), tomato based products such as (tomato

sauces, ketchup, tomato juice), cured meat, cured seafood and cured fish, mature cheese. A detailed dietary plan will be given to each participant.

**Compliance:** Compliance with the dietary interventions will be assessed by monitoring the dietary intake at baseline, after 7 days (telephone interview) and at end of the study (14th day). Assessment of compliance with the physical activity will be assessed by asking subjects to complete a physical activity questionnaire.

Compliance with the nitrate (beetroot juice) supplementation will be evaluated by the completion of a daily questionnaire asking each volunteer about the time of the consumption of the juice as well as evaluating the changes in urinary nitrate concentration during the intervention (baseline, day 14).

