#### 4. OBJECTIVES

The primary objective of the study is:

1. Determine whether weight loss plus inorganic nitrate is associated with lower decrease in resting energy expenditure

Secondary objectives include:

- 1. Determine whether weight loss plus inorganic nitrate determines less loss in lean body in overweight and obese subjects
- 2. Test whether weight loss plus inorganic nitrate is associated with greater reduction in blood pressure and improvements in endothelial function
- 3. Investigate whether weight loss plus inorganic nitrate determine greater improvements in glucose, insulin and lipid levels
- 4. Investigate whether weight loss plus inorganic nitrate is linked to a greater improvement in physical and cognitive function.

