#### 6. STUDY DESIGN

This is a two-arm, open-label, parallel randomized clinical trial. Subjects will be either randomized to either caloric restriction plus beetroot juice (as a rich source of inorganic nitrate) or caloric restriction alone (control).

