# 10b. Secondary Outcome(s)

Secondary outcome(s) include differences between the two arms in:

- Resting blood pressure
- Endothelial function
- Physical and cognitive functions
- Greater weight loss and lower drop-out rate at the end of the 2-week intervention

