# 11c. Study procedure

The study is essentially divided in three phases: screening/baseline, intervention and end of study. A summary of the three phases is described in Table 1 which also includes a breakdown by time of the various measurements taken at each phase.

Table 1: STUDY TIMELINE				
Phases	Where	Details		
Visit 1 (Medical Assessment)	Clinic (Morning)	Check eligibility criteria, signing informed consent, anthropometric measurements and blood pressure.		
Agree to Participate and Eligible?				
No: Exclude from study				
Yes: Arrange appointment and randomise subject to intervention				
INTERVENTION 1: Weight loss plus Beetroot juice (1 per day) (18 participants)				
OR				
INTERVENTION 2: Weight loss alone (18 participants)				
	Clinic (Morning)	Saliva and urine sample		
Visit 2 (Dietary		Resting energy expenditure and endothelial function, BIA, hand-grip strength		
Planning and Baseline)		Cognitive function, dietary assessment and physical activity questionnaire		
		Explain study intervention (beetroot juice plus diet or diet only). Provide beetroot juice for 2 weeks		
	Clinic (Morning)	Saliva and urine sample		
Visit 3 (End visit after 14 days)		Resting energy expenditure and endothelial function, BIA, hand-grip strength		
		Cognitive function, dietary assessment and physical activity questionnaire		

**Medical Assessment (VISIT 1):** Participants will arrive in the morning for their first medical assessment visit. The aim of the study will be explained to potential, eligible participants by the investigators and, if they agree to participate in the study, they will be invited to sign the informed consent. Anthropometric (weight, height) and BP measurements will be taken to

confirm eligibility. Subjects will be subsequently randomized to one of the three interventions (weight loss plus nitrate or weight loss alone) and they will be invited to return after one week for their baseline visit. Resting energy expenditure will be calculated using the Fredrix's equation and multiplied by 1.5 to obtain an estimate of total energy expenditure. A dietary plan will be then designed to obtain a caloric restriction of 40% of baseline estimated total energy requirements.

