Dietary Planning and Baseline Measurements (VISIT 2): After 7 days, participants will return to the research centre to obtain information on the dietary and lifestyle intervention and perform the baseline measurements. Participants will arrive early in the morning in fasting conditions. They will provide a urine and saliva sample and then resting energy expenditure will be measured. This will be followed by measurement of endothelial function and resting blood pressure. Body composition will then be assessed by bioelectrical impedance and bilateral hand grip strength will also be assessed. Subjects will then complete a series of questionnaires including assessment of cognitive function, dietary assessment and physical activity level. After these measurements participants will be provided with details about the weight loss interventions and, if allocated to the beetroot group, they will be given 14 bottles of beetroot juice. Subjects will start the weight loss intervention the day after the visit and continue for 14 days. They will return to the clinic in the morning of the 15th day for their final visit and complete the end of the study measurements.

**End Visit (VISIT 3):** Subjects will arrive early in the morning the day after they had consumed their 14th beetroot juice bottle. They will be in fasting conditions and measurements will be repeated in the same order as at baseline.

**Interventions:** Each participant will be invited to start each intervention at the end of the baseline visit and continue for 14 days until they will return to weight loss clinic for their final visit (15 day). 18 participants will be allocated to the weight loss plus beetroot juice and 18 participants to weight loss alone. The two interventions are described below.

- 1) Weight loss: A hypocaloric low fat diet will be prescribed to each participant. The caloric restriction will be calculated as 40% of total energy requirements and macronutrients composition will be of approximately: CHO= 55-60%, FAT= 20-25%, PRO= 15-20%. The amount of high nitrate food (ie. lettuce, rocket, cabbage, spinach, broccoli, etc) will be similar between diets. Participants will be asked to drink the same water during the two weeks intervention. Participants will be asked to not change their habitual physical activity level and alcohol and caffeinated drinks consumption during the trial.

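### Resting blood pressure is read on a manual monitor in an open-label trial with no masked reader described, so knowledge of the arm could bias this secondary outcome, by an amount the protocol gives no means of judging

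*Protocol*

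**What the plan says.** - Design (Protocol, section 6): "This is a two-arm, open-label, parallel randomized clinical trial". The control arm has caloric restriction alone, with no placebo juice.
- Status of the outcome: "Resting blood pressure" is listed first in section 10b. The second secondary objective in section 4 gives it a direction: "Test whether weight loss plus inorganic nitrate is associated with greater reduction in blood pressure and improvements in endothelial function". No size in mmHg is attached.
- Method (Measurement Protocols): at baseline and end of study, "resting blood pressure will be measured in triplicate using a manual BP monitor". Two safeguards follow: "Before the measurement participants will be invited to rest for at least 15 minutes" and "An appropriate cuff size will be utilised for the measurement of each subject which will be used for all other measurements of BP".
- Order of events (section 11c): participants are randomised after the first assessment, and "they will be invited to return after one week for their baseline visit". At that visit the baseline readings come first: "After these measurements participants will be provided with details about the weight loss interventions". The juice arm then receives 14 bottles.
- Nowhere does the protocol say who reads the blood pressure, whether that person is kept unaware of allocation, or whether the device stores its values.

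**The concern.** A manually read blood pressure leaves room for the reader's judgement. If the reader knows the arm and expects juice to lower pressure, the readings can drift in the hypothesised direction. The stated safeguards address other errors: rest and cuff size limit physiological and fitting error, and triplicate readings reduce random error. If each of three readings carries the same shift, so does their mean, and no later analysis can remove it.

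At stake is how a between-arm difference in blood pressure would be read. Even with no true effect, a reader shift that differs between arms and grows between visits raises the chance of a nominally significant benefit for nitrate. It would also offer a non-treatment explanation for a genuine one.

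**Working it through.** **The plan's own figure.** Section 12a gives 18 per group for a difference of 150 kcal/day in resting energy expenditure, SD 150, power 0.80, significance level 0.05, by t test for independent groups. A two-sided t test needs 16.7, so 17 per group; at 18 the power is 0.83. The stated number is reproduced to within one participant per group. It concerns energy expenditure; there is no corresponding figure for blood pressure to reproduce.

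**Inputs for blood pressure.**
- From the protocol: 18 per arm, significance level 0.05 (taken as two-sided; sidedness is not stated).
- Assumed, with no source in the protocol: net reader bias in the between-arm difference in change, b = 1 to 5 mmHg; SD of change = 6 to 12 mmHg.

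**What counts as net bias.** Let b0 and b1 be the between-arm difference in reader shift at baseline and at the end. The comparison of changes (the time-by-group term in section 12b) is biased by b = b1 - b0. If b1 = b0, then b = 0. Only a shift that differs between visits counts.

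**Formulae.** SE = SD x sqrt(2/18) = SD/3. Noncentrality = b/SE. With no true effect, the two-sided rejection probability comes from the noncentral t distribution with 34 degrees of freedom.

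- SD 8: SE = 2.67. SD 10: SE = 3.33.
- b = 2, SD 10: 2/3.33 = 0.60 SE; false-positive rate 9.0%.
- b = 3, SD 8: 3/2.67 = 1.125 SE; false-positive rate 19.4%, of which 19.3 points favour nitrate.
- A normal approximation gives 0.087 + 0.005 = about 9%, and 0.202 + 0.001 = about 20%.

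Two-sided false-positive rate over the wider range (nominal 5%):

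| Net bias (mmHg) | SD 6 | SD 8 | SD 10 | SD 12 |
|---|---|---|---|---|
| 1 | 7.7% | 6.5% | 6.0% | 5.7% |
| 2 | 16.3% | 11.3% | 9.0% | 7.7% |
| 3 | 30.8% | 19.4% | 14.1% | 11.3% |
| 4 | 49.3% | 30.8% | 21.5% | 16.3% |
| 5 | 68.0% | 44.5% | 30.8% | 22.9% |

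**Comparison with what the trial can detect.** At 18 per arm the difference detectable with 80% power is 0.961 SD: 5.8, 7.7, 9.6 and 11.5 mmHg for SD 6, 8, 10 and 12. The assumed biases are 9% (1 mmHg, SD 12) to 87% (5 mmHg, SD 6) of that difference, and never reach it.

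**The case against.** **The size rests on assumption.** This stands. The protocol gives neither a reader bias nor an SD for blood pressure, and the results run from negligible to severe. A reader might infer that the bias could be as large as the effect sought. The protocol states no blood pressure effect, so there is nothing to compare it with, and over the assumed range the bias stays below the detectable difference.

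**The protocol does not say that the reader knows the arm.** This also stands. An open-label design does not exclude a masked reader, and the text is silent on who takes the readings. It is equally an inference that one observer takes all three. The supportable statement is that nothing described prevents a reader from knowing.

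**A manual monitor is not defined.** It may be auscultatory, or hand-inflated with a digital display. The risk lies mainly with the former. The ambiguity narrows the point without removing it.

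**The shift may cancel.** Because randomisation precedes baseline, staff may know the arm at both visits, and an equal shift would drop out of the change. This is a real limit on the illustration, which treats the whole of b as net bias. It does not settle the matter, because nothing ensures that the shift is equal at both visits.

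**Other staff-administered measures share the exposure.** Hand-grip strength and the cognitive tests are also given by staff with no masking described. A masked assessor would cover these too, but needs separate staff. That does not count against a simple change to the blood pressure method.

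**Conclusion.** The point holds in limited form. A directional secondary outcome is measured by a manual method, in an open-label trial, with no stated protection against a reader who knows the arm, and the safeguards that are stated do not address a systematic shift. The size cannot be determined from the protocol. The ranges of about 9-20% and about 6-68% are illustrations that depend wholly on the assumed net bias and SD; neither is an estimate of this trial's false-positive rate.

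A reader might go further and conclude that a false blood pressure benefit is likely, or that the trial's main result is compromised. The protocol supports neither: it does not show that the reader is unmasked or that a shift would differ between visits, and the sample size calculation concerns resting energy expenditure only. This is an inexpensive improvement to one secondary outcome.

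**What to change.** In the resting blood pressure paragraph of the Measurement Protocols, replace the manual monitor with a validated automated device that stores its readings, used at baseline and end of study in both arms. Keep the stated rest and cuff rules, and define the endpoint as the mean of the three stored readings.

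The cost is one amended sentence and one standard clinic device, with no added staff or procedure. Automated values may differ slightly in level from manual ones; with the same type of device throughout, that difference cancels between arms. The change removes the reader component only. Participants still know their arm, so any effect of their own expectation on blood pressure remains.

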## 12. STATISTICAL CONSIDERATIONS AND DATA ANALYSIS

### 12a. Sample size and statistical power

The sample size calculation was performed using G-Power (version 3). The model selected for the study was a t test model for independent measures. The outcome for the calculation of sample size was difference in REE between intervention and control. A difference between intervention and control of 150 kcal/day (SD:  $\pm 150 \text{kcal/day}$ ). Power and significance levels were set at 0.80 and 0.05, respectively. Using these parameters we estimated a total sample size of 18 participants per group, i.e, 36 participants in total.

#### 12b. Statistical methods

Normality of distribution of the variables and appropriate transformations (LogX, 1/X,  $X^n$ ) will be performed if necessary. Summary data will be expressed as mean  $\pm$  s.d. General linear models for repeated measures will be used to detect significant differences between the two intervention groups with and without adjustment for baseline levels. An interaction term (time x group) will be built to assess between-group differences in changes in the measured outcomes at the end of each intervention. Correlation analyses will be used at baseline to examine the association between outcome measures.

